Cardiometabolic Benefits of Potatoes Mediated Along the Gut-Vessel Axis in Adults with Metabolic Syndrome

I. Objectives

The *objective of this application* is to establish evidence that incorporation of potatoes into a diet pattern based on the *Dietary Guidelines for Americans (DGA)* enhances cardiometabolic health in persons with metabolic syndrome (MetS) by improving microbiota- and host-mediated metabolic responses along the gut-vessel axis. Our central hypothesis is that the inclusion of potatoes, as part of a *DGA*-based dietary pattern, will potentiate gut barrier function and attenuate postprandial hyperglycemia (PPH)-mediated impairments in vascular endothelial function (VEF). To test this, we will complete the following objectives: 1) define changes in gut barrier function in association with improved gut microbiota composition, increased fecal short chain fatty acid (SCFA) production, and decreased serum endotoxin, 2) define changes in postprandial glycemic responses and endotoxemia, and 3) define changes in gut hormones that promote glycemic control and changes in markers of oxidative stress in relation to improvements in endothelial vascular function, all following 2-week potato consumption. Upon completing this study, we anticipate novel evidence demonstrating gut-level benefits of a potato-containing diet to lower cardiometabolic risk in MetS adults.

II. Procedures

A. Study Design

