We will enroll equal numbers of male and female MetS adults ($n = 30$; 18-50 y) from the Columbus, OH area as we detailed¹ to complete a 2-arm, randomized controlled, cross-over trial. Participants will be randomized in 3-unit blocks to receive a *DGA*-based diet containing Russet Burbank potatoes (350 g/d; 260 kcal; 12.4 g resistant starch) or an energy-matched bagel that is nearly devoid of resistant starch. Our approach closely follows recommendations of the *DGA*² and entails high scientific rigor by providing all foods during each 14-d intervention. On day 0, 7, and 14 of each period, coinciding with when participants obtain prescribed foods, we will assess anthropometrics (weight, height, waist circumference) and blood pressure. At baseline (day 0) of each trial, fasting glucose, insulin, and endotoxin will be measured to verify stable health status. Following each 14-d intervention, participants will provide a fecal sample and undergo testing in the fasted state for metabolic endpoints, gut barrier function, and VEF. Then, they will receive a glucose challenge (75 g) to examine VEF in relation to PPH at 30 min intervals for 2 h. Gut permeability probes (sucralose, erythritol, lactulose, mannitol) will also be co-administered on day 14, and urine collected for 24-h. After completing a 2-wk washout period (i.e. to restore microbiota composition³), participants will receive the alternate treatment (i.e. *DGA* diet + potato or bagel) and repeat all procedures.

B. Study Subjects

Enrollment Criteria. MetS adults will be studied because of their impaired VEF in association with glucose intolerance.⁴ We will enroll those who are unmanaged (i.e. no drug therapy) and they will be required to meet these established MetS criteria⁵ to improve homogeneity of study outcomes: i) fasting glucose 100-126 mg/dL, ii) waist circumference >102 cm for men or >88 cm for women, and iii) fasting triglyceride >150 mg/dL. We anticipate that they may also fulfill other MetS criteria, specifically HDL-C (<40 mg/dL for men, <50 mg/dL for women) and elevated blood pressure⁶ (>120/80 mmHg); these will be considered for co-variate analysis. Other inclusion criteria are: i) non-smoker, ii) non-dietary supplement user (>1-mo), iii) free of gastrointestinal disorders, CVD,

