cancer, and iv) no recent use of antibiotics, or any medications affecting glycemia, lipidemia, or blood pressure. Participants having any of these ***exclusion criteria*** will not be enrolled: i) use of anti-inflammatory agents or probiotics, ii) vegetarian, gluten intolerant, carbohydrate-restricted diet, iii) alcohol intake >2 drinks/d, or iv) ≥ 7 h/wk of aerobic activity.

Power Calculation. Plasma glucose and FMD during the 2-h postprandial period ($AUC_{0-120\text{ min}}$) and fasting endotoxin following 14-d controlled feeding have been selected as the **primary outcome variables**. These endpoints had no gender differences ($P>0.05$) in our prior studies. PPH was also inversely related ($P<0.001$) to FMD.^{4,7} MetS adults had improved FMD following low-fat milk ingestion compared with rice milk ($AUC_{0-3\text{ h}}: 1150\pm145$ vs 908 ± 118 , CV=56%) and attenuated PPH.⁴ For this study, we predict that FMD_{AUC} will be 25% greater in DGA+Potato during the oral glucose challenge on day 14. Thus, 26 MetS subjects would be needed to detect a treatment effect with >80% power ($P<0.05$). We will therefore enroll 30 subjects to account for unexpected attrition and increase power. A similar power calculation was performed using endotoxin measured from MetS vs. healthy adults.¹ To detect a 25% predicted lowering of endotoxin, 22 MetS subjects would be needed. Based on our preliminary data, DGA+Potato could lower endotoxin by increasing vitamin C status in addition to alleviating gut dysbiosis in a resistant starch-dependent manner. This secondary hypothesis will be tested by measuring vitamin C on day 14 using our routine HPLC-ECD method.¹

Statistical Analysis Plan

Most data in will be analyzed by linear mixed effects models (LMMs) with random effect for subjects (to account for repeated measures) and fixed effects for gender, time period, and their interactions. Multivariate regression analysis will define pairwise correlations between study variables in the presence or absence of potential study covariates. Statistical significance for all analyses will be set at $P<0.05$.

C. Detailed Study Procedures

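### Measuring day-14 vitamin C in a two-diet crossover can count against the vitamin C route to lower endotoxin, but it cannot establish that route

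*Combined protocol and SAP*

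**What the plan says.** Section II.A describes a "2-arm, randomized controlled, cross-over trial". One diet supplies potato with 12.4 g/d of resistant starch; the other supplies an "energy-matched bagel that is nearly devoid of resistant starch".

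Section II.B, Power Calculation, makes fasting endotoxin after 14 days a primary outcome. It then gives a two-route explanation for a fall in endotoxin: "DGA+Potato could lower endotoxin by increasing vitamin C status in addition to alleviating gut dysbiosis in a resistant starch-dependent manner". The stated test is: "This secondary hypothesis will be tested by measuring vitamin C on day 14 using our routine HPLC-ECD method".

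The Statistical Analysis Plan lists mixed models with a random subject effect and fixed effects for gender, time period and their interactions. It adds regression to describe correlations between pairs of study variables, with or without covariates that it does not name. It names no diet term and no mediation model. Under II.A, the day-0 laboratory measures are described as "fasting glucose, insulin, and endotoxin will be measured to verify stable health status"; vitamin C is not among them.

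**The concern.** The hypothesis is causal and has two routes, but the stated test is one measurement on one of them. That measurement can answer whether the potato diet raises vitamin C. It does not answer whether vitamin C is why endotoxin falls, because the other proposed cause arrives with the same diet.

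If both changes appear, the plan's wording invites the statement that the vitamin C hypothesis was tested and supported. A correlation between the two variables, computed without diet in the model, would seem to confirm it even if vitamin C did nothing. What is at stake is the explanation offered for a primary outcome. The randomised comparison of endotoxin between diets is not affected.

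**Working it through.** **1. What each explanation predicts after potato compared with bagel.**

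| True route to endotoxin | Vitamin C | Endotoxin |
|---|---|---|
| Vitamin C only | higher | lower |
| Resistant starch only (potato also raises vitamin C) | higher | lower |
| Both | higher | lower |
| Potato does not raise vitamin C | no difference | any fall must come by another route |

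The first three rows cannot be told apart by the diet contrasts. Only the fourth is informative, and it counts against the vitamin C route. The rise in vitamin C is the plan's own prediction; neither diet's vitamin C content is stated.

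**2. Size of the endotoxin shift implied by the plan.** The plan gives 22 subjects for a 25% lowering but no SD, so the figure cannot be reproduced. It can be inverted. Assuming a paired t test, two-sided 5% and 80% power, n = 22 corresponds to a mean difference of 0.63 SDs of the within-person difference (normal approximation: (1.96 + 0.84)/√22 = 0.60). The SD of a difference is SD × √(2(1 − ICC)), where ICC is the intraclass correlation. At ICC 0.5 this is 1.00 SD, so the shift is 0.63 SD. At ICC 0.7 it is 0.775 SD, so the shift is 0.63 × 0.775 = 0.49 SD.

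**3. What a correlation without diet would show.** Let dC and dY be the potato-minus-bagel differences in vitamin C and endotoxin, simulated as independent across people, so there is no person-level link. A subject-adjusted association without a diet term is the regression of dY on dC through the origin. Its slope is Σ(dC·dY)/Σ(dC²), which is pulled away from zero by the product of the two mean shifts. The correlation of within-person differences subtracts those means first. Inputs: n = 30 from the plan; the shifts and ICC are assumptions.

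| ICC | Vitamin C shift (SD) | Endotoxin shift (SD) | Significant, no diet term | Significant, within-person differences |
|---|---|---|---|---|
| 0.5 | 0.8 | 0.63 | 46% | 5% |
| 0.5 | 1.0 | 1.0 | 88% | 5% |
| 0.7 | 0.8 | 0.49 | 60% | 5% |
| 0.7 | 1.0 | 1.0 | 99% | 5% |

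Smaller shifts give lower rates: with both at 0.5 SD the no-diet figure is about 19% (ICC 0.5) or 36% (ICC 0.7). A study-period term does not help: at ICC 0.5 with both shifts at 0.8 SD, the rate is 62% with or without it.

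**4. How far a diet term goes.** A second simulation (n = 30, 4,000 runs per scenario, its own assumed effects) let resistant starch be the only true route. With a diet term, the vitamin C–endotoxin association was significant in 4.5% of runs when people's responses on the two routes were independent. It was significant in 12% and 29% when half and nine-tenths of the response variance was shared. When vitamin C was the only true route, it was detected in about 35% of runs. Adding diet removes the artefact in step 3, but the remaining association is neither free of confounding nor well powered.

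**The case against.** The hypothesis is hedged and labelled secondary, and no decision rule says that endotoxin will be attributed to vitamin C. That is fair; the objection here is to calling the measurement a test of the two-route statement. The measurement is also a legitimate check of a necessary condition, which stands and is a reason to keep the assay.

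The unnamed covariates could include diet, and the mixed models do include subjects. That is possible, but the plan does not say so, and the result depends on it.

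Three stronger readings are tempting, and the documents do not support them.

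- A reader might infer that the trial holds no information to separate the routes. Only assigned resistant starch coincides exactly with diet. Vitamin C, fecal short-chain fatty acids and microbiota composition are measured responses that vary between people, so exploratory information exists under assumptions.
- A reader might take a simulated rate as the plan's error rate. The plan fixes no model precisely enough to have one. A pooled correlation that ignores repeated measures gives about 20 to 38% at assumed shifts of 0.8 to 1.0 SD, but the plan does not name that test, and it already rejects about 8 to 12% with no diet shift.
- A reader might extend the point to the word mediated in the title. The title is framing; the numbered objectives in section I speak of changes in association with, or in relation to, one another, and diet effects on the gut measures are randomised contrasts.

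**Conclusion.** The concern holds in a limited form. The design can show that the potato diet changes vitamin C and that it changes endotoxin. It cannot attribute the second change to the first, because the resistant-starch route is predicted to move with the same switch and no analysis is specified to address this. A null vitamin C difference would still be informative.

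An association computed without a diet term would tend to appear whenever diet shifts both variables: about 46 to 99% of simulated trials for vitamin C shifts of 0.8 to 1.0 SD and endotoxin shifts from the size implied by 22 subjects up to 1.0 SD, against about 5% for within-person differences. Those rates rest on assumed shifts and ICC; their direction does not. The primary diet comparisons are untouched, so this is a change that should be made rather than a flaw in the trial's main result.

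**What to change.** - Restate the confirmatory part of the hypothesis as a diet effect: day-14 vitamin C is higher after DGA+Potato than after DGA+Bagel.
- Analyse the vitamin C–endotoxin relation as an exploratory association of within-person (potato minus bagel) differences, or equivalently in a model with subject, period and diet terms. Name that model in the Statistical Analysis Plan.
- Limit the conclusion to the potato diet as a whole, and say that an endotoxin effect will not be attributed to vitamin C or to resistant starch. Say also that no difference in vitamin C would count against the vitamin C route.
- Add vitamin C to the analyte list under Sampling Handling, where it does not now appear.

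This needs no new arm, visit or assay beyond the one already promised, and the primary analyses do not change. The cost is a weaker claim about mechanism.

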Test trials. At the end of the intervention period (day 14), participants will report back to the laboratory in the fasted state (10-12 hours) for assessment of height, weight, waist circumference, blood pressure, serum glucose, serum insulin, and serum endotoxin. Participants will return a stool sample collected on day 13 of the intervention period at home. Participants will ingest a sugar solution containing 75 g glucose, which we and others have routinely shown to induce PPH, oxidative stress, and VED. This will be co-ingested with 1 g sucralose, 1 g erythritol, 1 g mannitol, 5 g lactulose for assessment of gut permeability. Then, at 30 min intervals during the 2 h postprandial period, we will assess blood markers and brachial artery flow-mediated dilation. During each study visit, participants will have access to drinking water and use of the restroom as needed. Urine will be collected during the 2 h postprandial period in the laboratory, and participants will be instructed on urine collection for when they return home following their laboratory visit. Participants will return to the study center the following day to drop off their 24-h urine collection containers. To ensure that the order by which each participant completes each trial is randomized, a random sequence generator (<http://www.random.org/sequences/>) will be used to determine the order by which each participant will undergo the two trials.

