Sugar Probe Test. On the morning of testing at day 14, participants will arrive at the study center after abstaining from food and only consuming water for 10-12 hours. A sugar probe test will be conducted as described.⁹ Upon arrival, participants will be asked to empty their urinary bladder. Subsequently, they will then be asked to ingest a drink containing 1 g sucralose, 1 g erythritol, 1 g mannitol, and 5 g lactulose dissolved in a 75 g glucose solution (240 mL). Within 2-hours after ingesting the sugar test beverage, participants will be asked to consume an additional 500 mL of water. Additionally, participants will be provided with standardized sucrose-, erythritol-, lactulose-, and mannitol-free meals (e.g. English muffin, butter, scrambled eggs) during the 24-h period. All foods consumed during the 24-hour period will be free of artificial sweeteners. Urine will be collected from 0-5 and 6-24 hours in sterile containers. For each urinary collection period, participants will be provided 2-L urine collection containers and an insulated bag with ice packs to store collected urine until they return their samples the next day.

Sampling Handling. At each time point of the postprandial trial and once at baseline, a blood sample (20 mL; 1.4 tablespoons x 5 time points = 100 mL or 0.42 cups) will be collected into evacuated blood collection tubes. Collecting a total of 100 mL or 0.42 cups during the postprandial trial and once at baseline is necessary to ensure adequate amount of plasma for each time point to accurately analyze levels of glucose, insulin, endotoxin and gut hormones. During blood collection, participants may feel an initial pain when inserting the needle, bruising around the insertion area, lightheadedness, or fainting, which are common when donating blood. However, we do not foresee any additional significant risks for collecting this amount of blood over 2 hours, other than the risks stated previously.

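### For outcomes read five times per visit, a random effect for subjects alone leaves visit-to-visit variation out of the error for the diet main effect; the AUC and fasting primary outcomes are unaffected

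*Combined protocol and SAP*

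**What the plan says.** The model is specified in one sentence of the Statistical Analysis Plan, at the end of section II.B. Most of the data, with no outcomes named, go into "linear mixed effects models (LMMs) with random effect for subjects (to account for repeated measures"), with "fixed effects for gender, time period, and their interactions". The sentence gives no visit-level random effect and no within-visit covariance. It lists no diet term, and its time period could mean either crossover period or sampling time.

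The design produces two levels of repetition:

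- Section II.A describes a two-diet crossover, so each participant has two day-14 test visits.
- Section II.C, Test trials, says that "at 30 min intervals during the 2 h postprandial period, we will assess blood markers and brachial artery flow-mediated dilation". With the fasted reading this makes five: 0, 30, 60, 90 and 120 min. Sampling Handling agrees ("1.4 tablespoons x 5 time points = 100 mL") and names glucose, insulin, endotoxin and gut hormones as the analytes.

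The Power Calculation paragraph names three primary outcomes: glucose AUC and FMD AUC over 0 to 120 min, and fasting endotoxin. Each is one number per visit. The plan defines no per-visit summary for the other postprandial markers, although Objective 2 is to "define changes in postprandial glycemic responses and endotoxemia" and Objective 3 concerns gut hormones and oxidative stress markers.

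**The concern.** A subject intercept makes all ten of a person's readings equally correlated. It allows nothing extra for what the five readings of one visit share, such as that day's fasting level, probe placement or assay run. Diet is constant within a visit, so a shift common to one visit cannot be told apart from a diet effect in that person. That variation therefore belongs in the error for the diet main effect. If the model omits it, the standard error for diet is too small and chance differences between visits are reported as diet effects.

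At stake are the secondary postprandial outcomes: endotoxin, insulin, gut hormones, oxidative markers if they are measured at each draw, and any time-course analysis of glucose or FMD.

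**Working it through.** **Inputs from the documents.** 30 participants; 2 test visits; 5 readings per visit; nominal level 0.05 (taken as two-sided, since sidedness is not stated).

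**Inputs assumed.** A diet term is in the model, because the plan intends to detect a treatment effect. The readings follow: sampling time + subject + visit within subject + error, with visit variance σv² and error variance σe². Let p = σv²/(σv² + σe²) be the visit share of within-person variance. The documents give no value, so a range is shown. Scale σv² + σe² to 1.

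**The plan's own figures.** The plan gives no figure for time-course tests beyond the nominal 5%, which the calculation returns at p = 0. Its sample size of 26 concerns FMD AUC, one value per visit, and does not enter here.

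**Degrees of freedom.** There are 30 × 2 × 5 = 300 readings. Removing 1 for the mean, 29 for subjects, 1 for diet, 4 for time and 4 for diet-by-time leaves 261. Of these, 29 are between visits and 232 within visits. A period term would take one from the 29, which is immaterial.

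**Mean squares.**

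- Correct error for the diet main effect: σe² + 5σv² = 1 + 4p.
- Error used with a subject intercept alone: [29(σe² + 5σv²) + 232σe²]/261 = σe² + 5σv²/9 = 1 − 4p/9.
- With R = (1 + 4p)/(1 − 4p/9), the diet SE is too small by a factor √R, and the type I error is approximately 2[1 − Φ(1.96/√R)].
- Correct error for diet-by-time: σe² = 1 − p, which is smaller than 1 − 4p/9, so that test is conservative.

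**Example at p = 20%.** R = 1.80/0.911 = 1.976 and √R = 1.41. Then 1.96/1.41 = 1.39, whose two-sided tail is about 16%. The diet-by-time SE is too large by √(0.911/0.80) = 1.07.

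| Visit share p | 1 + 4p | 1 − 4p/9 | √R | Diet, approximation | Diet, simulated | Diet-by-time, simulated |
|---|---|---|---|---|---|---|
| 0% | 1.00 | 1.000 | 1.00 | 5.0% | 5.0% | 5.0% |
| 5% | 1.20 | 0.978 | 1.11 | 7.7% | 7.7% | 4.5% |
| 10% | 1.40 | 0.956 | 1.21 | 10.5% | 10.6% | 4.0% |
| 20% | 1.80 | 0.911 | 1.41 | 16.3% | 16.3% | 3.0% |
| 30% | 2.20 | 0.867 | 1.59 | 21.9% | 21.8% | 2.0% |
| 50% | 3.00 | 0.778 | 1.96 | 31.8% | 31.7% | 0.65% |

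The simulated columns draw the mean squares 400,000 times per row. With 26 participants the diet results agree to within 0.1 point.

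**Checks.**

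- *Fitted models.* REML fits with a subject intercept alone (300 trials per setting, simulation SE about 2 points at p = 20%) rejected 5.7% at p = 0, 12.7% and 14.7% at p = 20% under two assumed subject variances, and 33% at p = 50%. A separate 150 fits at p = 20% rejected 21% (SE about 3 points). These scatter around the table and are too few to refine it.
- *Remedy.* A subject-by-visit random effect, or one summary per visit, gives 5.0% at every share tried.
- *Number of readings.* With four readings instead of five, the two mean squares become 1 + 3p and 1 − 3p/7. At p = 20%, R = 1.60/0.914 = 1.75, √R = 1.32, and the type I error is about 14%.
- *AR(1) alone.* A subject intercept plus within-visit AR(1), at its best large-sample fit to these data, still gives about 8, 11 and 15% at p = 10, 20 and 50%. Its correlation decays with lag, whereas a shared visit shift does not.

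**The case against.** The strongest reply is that the plan does not state an invalid model. It never says that the random effect is an intercept or the only covariance term, and a one-sentence summary leaves the residual structure open. It names no outcome to be analysed reading by reading. Glucose and FMD are summarised as AUC, and the other markers might be treated the same way. The model lists no diet term, so it cannot be said that the standard error for diet, as written, is too small. The sizes rest entirely on assumed visit shares.

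All of this stands, and it rules out three stronger readings that a reader might infer:

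- *The plan commits to an intercept-only model.* That is the natural reading of the sentence, but it is an inference.
- *Every diet test on a time course is inflated.* Only the diet main effect is. The diet-by-time test is conservative, and markedly so at high visit shares.
- *Objectives 2 and 3 are undermined as a whole.* Glucose AUC serves the glycemic part of Objective 2 and FMD AUC the vascular part of Objective 3. Both have one value per visit.

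The reply does not remove the point. The sentence assigns the handling of repeated measures to the subject effect and names nothing else, so an analyst who follows it literally fits the model examined here. Intending a diet test while omitting its term is a further gap in the same sentence and does not repair the error structure. Zero visit variance is possible, but it is implausible for readings that share one day's fasting level.

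**Conclusion.** The concern holds conditionally. If outcomes with five readings per visit are analysed at reading level with a subject intercept alone, the diet main-effect test is anti-conservative. Its type I error is about 8% at a 5% visit share, 16% at 20% and 32% at 50%, against a nominal 5%.

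This rests on 30 participants with complete data, five readings per visit, a visit effect shared equally by those readings, a diet term that the plan does not list, and visit shares that the documents do not supply. The direction of the error is certain whenever visit variance exceeds zero; its size is not. The consequence is confined to secondary time-course outcomes. The documents do not support any claim that the three primary analyses or the stated sample size are affected by this point.

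**What to change.** Replace the model sentence with text to this effect:

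- *Outcomes read more than once per visit:* fixed effects for diet, period, sampling time and diet-by-time (with gender as planned), and random intercepts for subject and for subject-by-visit. An unstructured within-visit covariance may replace the visit intercept, but AR(1) alone may not. Use a small-sample degrees-of-freedom correction such as Kenward-Roger. Alternatively, analyse one summary per visit, such as AUC. State which route applies to each outcome.
- *AUCs and single fasting values:* keep the subject-only random effect, with diet and period named as fixed effects.

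An unstructured 5 × 5 covariance has 15 parameters to estimate from 60 visits, so the visit intercept is the safer default.

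The change costs a few lines of SAP text, with no new data or participants, and should be made before the codes are broken. The downside is wider intervals for the diet main effect on secondary time-course outcomes, by a factor of about 1.4 at a 20% visit share. Diet-by-time tests regain the power that the subject-only model gives away.

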Overview of Study Procedures. Potential participants who call the study center in an anonymous manner for more information as well as those identified through ResearchMatch will be given a brief description about the study and asked a few questions to determine their eligibility (see *Phone Script* attachment). If they meet the eligible criteria, they will be invited to the study center for a screening meeting. During the meeting, the Informed Consent (see *Informed Consent* attachment) will be explained and provided for them to review. The participant will then be given the opportunity to review the Informed Consent form. If he/she chooses to participate in the study, they will then be asked to provide written consent. Women choosing to participate will also be asked to complete the *Menstrual History Questionnaire*. After receiving informed consent, the participants' height, weight, waist circumference, and blood pressure will be measured. Additionally, a small fasting blood sample will be collected for blood chemistry analysis. If they are not fasted at least 10 hours, they will be asked to come back in the fasted state at time of mutual convenience. These blood results in combination with anthropometric parameters will determine the participant's eligibility. Eligible participants who agree to proceed with the study will then complete two 2-week intervention periods in a randomized order, each followed by a 2-h postprandial trial. We estimate that completion of all study procedures will take ~6-12 weeks per participant. Each step of the study procedure will be discussed in detail below:

Screening Meeting. Potential participants who have met the initial criteria of the study (based on the telephone interview) will be invited to the study center at a mutually convenient time. During this time, the participant and a member of the research team will meet in a private, quiet conference room or office. The individual will be provided the informed consent form, and its contents will be

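### The only stated outcome model has no diet term, so run as written it gives no potato-versus-bagel estimate for any of the three primary outcomes.

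*Combined protocol and SAP*

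**What the plan says.** Section II.B, Statistical Analysis Plan, specifies one outcome model, meant for most data: a linear mixed model "with random effect for subjects (to account for repeated measures) and fixed effects for gender, time period, and their interactions". The only other analysis named there is a multivariate regression for pairwise correlations between variables. Neither sentence mentions diet, treatment, arm or sequence.

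Elsewhere the plan is built around a diet comparison:
- II.B, Power Calculation, makes glucose AUC, FMD AUC and fasting endotoxin after 14 days of feeding the primary outcomes, and says that "26 MetS subjects would be needed to detect a treatment effect with >80% power".
- II.C, Overview of Study Procedures, has participants "complete two 2-week intervention periods in a randomized order".
- II.A, Study Design, says "Participants will be randomized in 3-unit blocks" and "We will enroll equal numbers of male and female MetS adults", with 30 in total.

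The word period carries more than one meaning. It is the cross-over period in "On day 0, 7, and 14 of each period" (II.A) and the two hours after the glucose drink in "Plasma glucose and FMD during the 2-h postprandial period" (II.B).

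**The concern.** In a two-arm cross-over, the model term for the randomised factor is what answers the trial's question. The written model leaves it out and keeps gender, for which the Power Calculation reports no differences in the group's earlier studies. No other section supplies the missing contrast.

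Two things are at stake. First, an analyst who follows the text literally tests gender and period only. The diet effect then inflates the residual and, with unequal order groups, can be misread as a period effect. Second, and more realistically, the analyst adds a diet term after the fact. Choices such as whether to adjust for period, whether to include diet by sex, and whether to use AUCs or 30-minute values would then be made without a written rule, for three primary outcomes.

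**Working it through.** **1. What each reading of time period estimates**

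| Reading | What the term compares | Potato versus bagel? |
|---|---|---|
| Cross-over period | Period 2 with period 1, each containing both diets because order is randomised | No |
| Postprandial sampling time | Nothing for the primary outcomes: an AUC or a fasting value is one number per visit | No |
| Study day 0 or 14 (endotoxin only) | Change over feeding, averaged over both diets | No |

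The interactions can only combine the listed terms, so they add no diet term either.

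**2. The plan's sample size presupposes the missing term**

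Inputs from the Power Calculation: effect 25%, CV 56%, power 80%, P<0.05 (taken as two-sided). For a paired t-test, SD of the difference = 0.56 × √(2(1 − ρ)), where ρ is the within-subject correlation. The plan gives no ρ. The required n is 81, 42, 34, 26 and 18 at ρ = 0, 0.5, 0.6, 0.7 and 0.8. The stated 26 is therefore reproduced only at an assumed ρ of about 0.70. Parallel groups would need 79 per arm. So 26 makes sense only as the size for a within-subject diet contrast.

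**3. Where the diet effect goes under the cross-over reading**

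Let d be potato minus bagel, π the true period effect, a the number who start with potato and b the number who start with bagel. Period 2 minus period 1 has mean π − d in the first group and π + d in the second. Averaged over everyone, it is π − d(a − b)/(a + b). The period term therefore carries a share |a − b|/(a + b) of the diet effect.

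To put this on a power scale, take the effect that 26 subjects detect with exactly 80% power in a two-sided paired t-test: 0.572 SD of the within-subject difference (noncentral t). With 30 subjects, no true period effect and 400,000 simulated trials per split:

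| Split | Share of d in period term | Period effect declared, diet omitted | Power for diet, diet and period fitted |
|---|---|---|---|
| 15:15 | 0/30 = 0% | 2.5% | 85.7% |
| 16:14 | 2/30 = 6.7% | 2.7% | 85.4% |
| 18:12 | 6/30 = 20% | 5.2% | 84.2% |
| 20:10 | 10/30 = 33% | 11.2% | 81.3% |

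**4. Effect on the residual**

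The variance of the period difference rises by the factor 1 + 0.572² × 4ab/(a + b)². This is 1 + 0.327 = 1.33 at 15:15 and 1 + 0.327 × 0.889 = 1.29 at 20:10. That is why the period test rejects in fewer than 5% of trials when the groups are equal.

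A separate simulation fitted the written model (300 trials per split; assumed bagel mean 908, CV 56%, ρ 0.70, d = 0.25 × 908 = 227). The residual variance ratio was 1.28 to 1.35. The mean period coefficient was 0.6 at 15:15, −74 with 20 of 30 starting on potato (formula: −227 × 10/30 = −76) and +75 with 10 of 30. With diet added, the mean diet estimate was 225, 229 and 219 respectively.

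**5. Which split to expect**

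The plan states no split, and a block of three cannot be halved. If ten full blocks each have a randomly chosen majority order (assumption), 15:15 has probability C(10,5)/2¹⁰ = 252/1024 = 24.6%, 16:14 in either direction 420/1024 = 41.0%, and 20:10 in either direction 2/1024 = 0.2%. The mean share is 8.2%. If the majority order is the same in every block, the split is 20:10. With 15 men and 15 women, the best split within a sex is 8:7, so the period contrast within each sex carries at least 1/15 = 6.7% of the diet effect for that sex.

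**The case against.** A sponsor could fairly say that this is a drafting slip. The sentence is visibly incomplete, it speaks of interactions in the plural although two factors have only one two-way interaction, and the power text names a treatment effect. No competent analyst would report this trial without a diet term. The sponsor could add that period might mean the intervention period, labelled by diet; that the model covers only most data; that endotoxin also has a day-0 value; and that a 20:10 split is improbable if block majorities are random. II.C, Test trials, also assigns order by a random sequence generator without mentioning blocks.

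Some of this stands. The intent is clear, so a published analysis with no diet term is unlikely. The leakage figures depend on a split that the documents do not give, and for near-equal groups the leakage is small. The power figures are back-calculated from the stated 26 at exactly 80% power.

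The core is not answered. Reading time period as a diet label is unnatural, and the plan nowhere defines it so. Most data may leave room for another analysis, but none is described for any primary outcome. The day-0 endotoxin value gives a time effect, not a diet effect. Clear intent does not settle which model and which contrast are primary.

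**Conclusion.** The concern holds. None of the listed terms estimates diet, and this needs no assumption. Taken literally, the plan cannot test its central hypothesis on any of the three primary outcomes.

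The secondary consequences are conditional. The period term carries between 0% (15:15) and 33% (20:10) of the diet effect, averaging 8.2% if block majorities are random. With the assumed 0.572 SD effect and no true period effect, a period effect is declared in 2.5% to 11.2% of trials. Once diet is fitted, 30 subjects give about 86% power at 15:15 and 81% at 20:10 for that same effect. The design can therefore answer the question, and the defect lies in the written model. It must be corrected before analysis.

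**What to change.** Replace the model sentence with wording such as: For each primary outcome (glucose AUC 0–120 min, FMD AUC 0–120 min, day-14 fasting endotoxin; one value per cross-over period), a linear mixed model with fixed effects for diet, cross-over period and sex and a random effect for subject; the diet coefficient with its 95% CI is the primary estimate.

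Define period as first or second intervention period, and use a different word for postprandial time. A sequence term is optional, diet by sex can be a secondary term, and the planned gender-by-period interaction may stay; the repair does not depend on any of these.

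If 30-minute values are modelled directly as a secondary analysis, also add time, diet by time, and either a subject-by-period random effect or a within-visit covariance structure. With a subject-only random effect, the simulated type I error of the time-averaged diet effect is 10.5% to 31.7% when visits account for an assumed 10% to 50% of within-subject variance. The documents give no such share, and the primary outcomes are unaffected.

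The cost is SAP wording and one degree of freedom for diet in each primary model, with a few more in any time-course model. No new data or visits are needed.
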